6. ENDPOINTS AND COVARIATES

6.1. Safety Endpoints

- Adverse drug reactions: Adverse events determined to be related to Vfend by the physician
- Adverse events: All-causality adverse events
- Serious adverse events or adverse drug reactions: Adverse events or adverse drug reactions determined to be serious by the physician.
- Important identified risks determined to be safety specifications are listed below.
 - Hepatic toxicity
 - QT prolongation, ventricular tachycardia, ventricular fibrillation, arrhythmia, complete atrioventricular block
 - Visual events
 - Phototoxicity
 - Peripheral neuropathy such as Guillain-Barre syndrome
 - Renal disorder
 - Hematologic disorder
 - Interstitial pneumonia
 - Cardiac failure
 - Consciousness disorder

Specific event terms to be handled as safety specifications will be specified separately.

- Events to be handled as major investigation items are listed below.
 - Hepatic toxicity
 - Visual events

6.2. Effectiveness Endpoints

- Clinical response: Clinical response will be assessed based on clinical course excluding mycological response.
 - Effective
 - Not effective
 - Indeterminate
- Mycological response
 - Eradication: The causative fungi detected from the focus before treatment with this product has become negative

- Presumed eradication: In the case when the focus improved and the collection of test material became impossible
 - Decreased: The causative fungi decreased
 - No change: There is no change in causative fungi
 - Increased: The causative fungi increased (including the case of microbial substitution)
 - Indeterminate: In the cases when the follow-up was inadequate, the causative fungi were not detected, or the mycological test was "not conducted"
- Eradication of causative fungi

The eradication of causative fungi will be assessed by causative fungi based on the eradication of causative fungi obtained at or before the initiation of treatment after administration of Vfend using the results of mycological testing such as culture, microscopy, histopathological test, and genetic diagnosis in the safety analysis set.

- Eradication: The volume of the causative fungi after treatment with Vfend is “-” or a specimen cannot be collected.
- Persistence: The volume of the causative fungi after treatment with Vfend is “+” or higher.
- Indeterminate: All mycological tests after treatment with Vfend are “not performed” or the volume of the causative fungi is “unknown.”

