7.7. Data analysis

The details of analysis method on data collected in this study shall be described in the Statistical Analysis Plan to be separately prepared.

1) Definition of analysis set

The safety analysis set shall include patients for whom the registration in this study and administration of this product have been confirmed.

Two analysis sets, which are clinically-evaluable analysis set and mycological analysis set, shall be defined as the effectiveness analysis set. The clinically-evaluable analysis set includes patients for whom performance of clinical response was confirmed among patients in the safety analysis set. The mycological analysis set include

patients for whom microbiological response was assessed among patients in the clinically-evaluable analysis set.

2) Analysis method

(1) Safety analysis

The incidence of adverse reactions shall be calculated for each event. Also, the factors affecting the occurrence of adverse reactions shall be evaluated as necessary.

(2) Effectiveness analysis

The clinical response rate (the number of responders / the number of clinically-evaluable patients excluding indeterminate patients) and its 95% confidence interval shall be calculated for the clinically-evaluable analysis set. Also, the eradication rate (the number of patients with mycological eradication + presumed eradication / the number of patients for mycological analysis excluding indeterminate patients) and its 95% confidence interval shall be calculated for the mycological analysis set.

Detailed methodology for summary and statistical analyses of data collected in this study will be documented in a Statistical Analysis Plan of this study and maintained by Pfizer. The SAP may modify the plans outlined in the protocol; any major modifications of primary endpoint definitions or their analyses would be reflected in a protocol amendment.

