5. ANALYSIS SETS

5.1. Safety Analysis Set

The safety analysis set is defined as the full analysis set that is as close as possible to all patients treated with Vfend. More specifically, the safety analysis set is defined as the population of patients registered or reported, excluding patients who meet at least one of the following conditions:

- a. The case report form could not be collected at all (description in the report, “case report form not collected”)
- b. There was a violation or deficiency in the contract (description in the report, “contract violation/deficiency”)
- c. There was a violation of registration (description in the report, “registration violation”)
Aged ≥ 15 years at the initiation of treatment
- d. Administration of the drug under investigation is not reported at all (description in the report, “no administration information”)
- e. Information on adverse events is not reported at all - no visits after the first prescription day (description in the report “no adverse event information - no revisits”)
- f. Information on adverse events is not reported at all - there is a visit after the first prescription day but no description of safety information (description in the report, “no adverse event information - no description”)

“Guidance for Criteria for Inclusion in Analysis Sets and Data Handling in Drug Use Investigations” will be followed for the details of each criterion.

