5.2.2. Mycological Analysis Set

The mycological analysis set is defined as the population of patients in the safety analysis set for whom the final diagnosis is invasive fungal infections or invasive fungal infections

suspected and data for mycological response evaluation (mycological response at the end of the observation period) were collected. The mycological analysis set is defined as the population of patients in the safety analysis set, excluding patients who meet at least one of the following conditions:

- i. Disease other than the target diseases of the study (final diagnosis is “others”; description in the report, “non-target disease”)
- j. Mycological response is not reported at all (description in the report, “no information on mycological response”)

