8.2.4.2. Mycological Response

In the mycological analysis set, the number and proportion (eradication rate) of patients for whom mycological response was determined as eradication or presumed eradication and the

95% confidence interval will be calculated. The formula to calculate the eradication rate is shown below.

$$\text{Eradication rate (\%)} = \frac{\text{the number of patients with mycological eradication + presumed eradication}}{\text{the number of patients in the mycological analysis set excluding indeterminate patients}} \times 100$$

The eradication rate will be calculated also by diagnostic name (name of infection) (definitive diagnosis + suspected cases) and by diagnostic name [definitive diagnosis] (name of infection).

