8.2.4.3. Mycological response by Causative Fungus

The number and proportion (eradication rate) of fungus for which eradication after treatment with Vfend was determined as eradication and the 95% confidence interval will be calculated by causative fungus identified at the initiation of treatment. The formula to calculate the eradication rate is shown below.

$$\text{Eradication rate by causative fungi (\%)} = \frac{\text{the number of eradicated fungi}}{\text{the number of (eradicated + persistent) fungi}} \times 100$$

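### Eradication by causative fungus is assessed in the safety analysis set, so fungi from children whose final diagnosis is neither confirmed nor suspected invasive fungal infection can enter an effectiveness rate

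*SAP*

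**What the plan says.** SAP 6.2 lists eradication of causative fungi as an effectiveness endpoint beside clinical and mycological response. It is judged fungus by fungus, "using the results of mycological testing such as culture, microscopy, histopathological test, and genetic diagnosis in the safety analysis set". SAP 8.2.4.3 turns it into a rate for each fungus identified at the start of treatment, with denominator "the number of (eradicated + persistent) fungi". That section names no analysis set and no diagnosis filter, so the population in 6.2 governs.

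SAP 5.1 makes the safety set deliberately broad: "The safety analysis set is defined as the full analysis set that is as close as possible to all patients treated with Vfend". Its exclusions a to f cover an uncollected case report form, contract problems, registration violation, no administration information, and two forms of absent adverse event information. The one registration violation it spells out is "Aged ≥ 15 years at the initiation of treatment".

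The patient-level eradication rate is built differently. Its denominator is "the number of patients in the mycological analysis set excluding indeterminate patients" (SAP 8.2.4.2). SAP 5.2.2 limits that set to patients "for whom the final diagnosis is invasive fungal infections or invasive fungal infections" suspected. Exclusion i removes "Disease other than the target diseases of the study (final diagnosis is" *others*), and exclusion j removes patients with no mycological response reported.

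SAP 5.2 names two effectiveness sets, clinical response and mycological, and SAP 5.3 adds none. Protocol 7.7 defines its mycological set as "patients for whom microbiological response was assessed among patients in the clinically-evaluable analysis set" and has no by-fungus endpoint.

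**The concern.** The SAP reports two results that it calls an eradication rate, one per patient and one per fungus. The first is confined to children with a confirmed or suspected invasive fungal infection. The second, as written, is open to fungi from any child in the safety set, including those whose physician finally concluded that the disease was not a target disease of the study.

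Whatever happens to a fungus in such a child, it does not show whether Vfend clears invasive fungal infection, which is what the endpoint is for. A reader of the final report would not be told that the two rates rest on different diagnostic populations. Rows for single fungi are likely to be short, so one or two ineligible isolates could visibly change a row.

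**Working it through.** **1. The two rates side by side**

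| | Patient-level rate | By-fungus rate |
|---|---|---|
| Population | Mycological analysis set (SAP 5.2.2, 8.2.4.2) | Safety analysis set (SAP 6.2); none named in 8.2.4.3 |
| Final diagnosis *others* | Removed (exclusion i) | Not removed |
| No mycological response reported by the physician | Removed (exclusion j) | Not removed |
| Unit | Patient | Fungus |
| Left out of denominator | Indeterminate patients | Indeterminate fungi |

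**2. Are children with final diagnosis *others* expected in the safety set?** Yes, on four grounds:

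- SAP 5.2.1 (exclusion h) and 5.2.2 (exclusion i) each remove non-target disease from the safety set, which presumes that such patients are in it.
- SAP 8.2.2 tabulates *others* as a diagnosis category in the safety set.
- SAP 5.4 uses the same category as a safety subgroup.
- Protocol 7.3.7.1 offers a diagnosis that is neither confirmed nor suspected invasive fungal infection as a ready-made reason for an indeterminate clinical response.

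**3. Can they contribute a fungus?** Yes. Protocol 7.3.4.1 records the assumed causative fungi used for diagnosis. The final diagnosis is a separate item (Protocol 7.3.5), and neither document applies it back to the isolate.

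**4. Size.** The documents give no isolate counts and no number of children with final diagnosis *others*, so the real effect cannot be computed. As an illustration, assume a row with 20 evaluable isolates from children with confirmed or suspected infection, 12 of them eradicated. Add m isolates from children with final diagnosis *others*, of which e are eradicated (0 ≤ e ≤ m):

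rate = (12 + e) / (20 + m)

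| m | None eradicated (e = 0) | All eradicated (e = m) |
|---|---|---|
| 0 | 12/20 = 60.0% | 12/20 = 60.0% |
| 1 | 12/21 = 57.1% | 13/21 = 61.9% |
| 2 | 12/22 = 54.5% | 14/22 = 63.6% |
| 3 | 12/23 = 52.2% | 15/23 = 65.2% |
| 5 | 12/25 = 48.0% | 17/25 = 68.0% |

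The rate rises only if e/m exceeds 12/20. With m = 2 both added isolates must clear, since one of two gives 13/22 = 59.1%. For scale, the exact 95% interval (the method of SAP 8.1.3) for 12/20 is 36.1% to 80.9%, so these shifts lie inside the sampling uncertainty of so short a row.

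**The case against.** The strongest case on the other side has five parts.

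- **Entry is already narrow.** Invasive fungal infection is a registration criterion (Protocol 7.2.1, 7.6.2), and only fungi assumed causative and used for diagnosis are recorded (Protocol 7.3.4.1). Suspected cases stay in the mycological set. A child with such a fungus who still ends as *others* may be rare. This stands as a limit on the number, but it does not close the gap: SAP 5.1 does not list absence of infection as a registration violation, and exclusions h and i would have no purpose if screening sufficed.
- **The direction is open.** A reader might infer that these isolates are colonisers or contaminants, that they disappear anyway, and that the rate is biased upward. The documents do not support this. Final diagnosis *others* means non-target disease, which need not mean that the fungus was harmless. Under SAP 6.2 a fungus with no test after treatment, or of unknown volume, is indeterminate and leaves the denominator. One that is retested may persist and lower the rate. One feature does point upward: 6.2 counts an uncollectable specimen as eradication, without the improved focus that patient-level presumed eradication requires. That does not settle the net direction.
- **The rate is reported by fungus.** A stray isolate affects its own row only. This stands; the illustration above describes one such row, not a pooled figure.
- **The consequence is modest.** SAP 4.1 and 4.2 make the study non-confirmatory with no decision rule, the two rates differ in unit anyway, and SAP 9 plans a mycological test listing in which isolates can be inspected. This lowers the weight of the point without removing it.
- **The safety set may be deliberate.** It keeps fungi with usable test results from children whose physician gave no mycological rating. The SAP states no such reason, but the advantage is real and the fix should preserve it.

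A reader might also infer a conflict with the protocol. There is none on this endpoint, because Protocol 7.7 defines no by-fungus rate and sets no final-diagnosis restriction.

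**Conclusion.** The point holds as a mismatch of populations within the SAP. Fungi from children with neither confirmed nor suspected invasive fungal infection are eligible to enter an effectiveness rate, through a set that the SAP does not declare for effectiveness, while the patient-level rate excludes those children.

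The size and sign of the effect are unknown. On the assumed 12/20, two added isolates move the rate to somewhere between 54.5% and 63.6%, and with no such isolates nothing changes. The change log for SAP version 3.0 cites the small number of patients evaluable for the eradication rate as its reason for dropping a subgroup analysis, so even a few isolates could matter within one fungus. This conclusion rests on reading 8.2.4.3 as taking its population from 6.2, since it names none of its own.

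This is a cheap improvement, not a flaw that undermines the study.

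**What to change.** In SAP 6.2, replace the reference to the safety analysis set by: *in patients in the safety analysis set whose final diagnosis is invasive fungal infection or invasive fungal infection suspected (exclusion i of 5.2.2 applied; exclusion j not applied, because this endpoint is derived from test results)*. State the same population in 8.2.4.3.

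Moving to the full mycological analysis set would go too far. It brings in exclusion j and would discard fungi with usable test results only because the physician's patient-level rating is missing.

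Isolates from children with final diagnosis *others* stay in the mycological test listing, so nothing is hidden.

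The cost is one phrase in each of two sections. Final diagnosis is already collected (Protocol 7.3.5), so no new data are needed. The downside is the possible loss of a few isolates from the denominator.

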7.3.7.2. Mycological response

The mycological response should be determined at the end of the observation period and the results should be recorded.

- Eradication: The causative fungi detected from the focus before treatment with this product has become negative
- Presumed eradication: In the case when the focus improved and the collection of test material became impossible
- Decreased: The causative fungi decreased
- No change: There is no change in causative fungi
- Increased: The causative fungi increased (including the case of microbial substitution)
- Indeterminate: In the cases when the follow-up was inadequate, the causative fungi were not detected, or the mycological test was "not conducted"

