9. LISTINGS

The following listings will be prepared. Listings with [Intext] specified after the table name are in a format which allows attachment to the report without change.

- Listing of patients^a

^a : Estimated creatinine clearance in the listing will be calculated from serum creatinine before the initiation of Vfend treatment using the Cockcroft-Gault Cr calculation formula. eGFR will also be calculated because the CDK guideline for children recommends calculation of eGFR. A quintic equation will be used for calculation of

-
- Listing of patients with adverse events (including events observed after the observation period and follow-up period)
 - Listing of patients with adverse drug reactions
 - Listing of patients with adverse drug reactions among patients excluded from the safety analysis set
 - Listing of patients with serious adverse drug reactions [Intext]
 - List of events corresponding to safety specifications including major investigation items
 - List of adverse drug reactions falling under safety specifications including major investigation items [Intext]
 - Listing of other reasons for discontinuation [Intext]
 - Listing of mycological test
 - Listing of laboratory values
 - Listing of serological test and imaging test
 - Listing of the record of administration of Vfend and plasma voriconazole concentration
 - Listing of prior medications (antifungal agents) by patient
 - Listing of concomitant medications by patient [Intext]
 - Listing of deaths [Intext]

Furthermore, the following tables corresponding to appendix tables for periodic safety report (PSUR) will be prepared:

- Appendix Form 16 (Overview of patients in post-marketing surveillance)
- Appendix Form 15 (List of development of adverse drug reactions and infections)
- Appendix Form 12 (Development of adverse drug reactions and infections in additional pharmacovigilance plan)

eGFR for children. (See Attachment 10.3) The quintic equation is for patients aged 2 to 19 years but will be used also in patients aged <2 years.

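### SAP 6.2 counts a causative fungus as eradicated whenever no specimen can be collected, without requiring an improved focus as the patient-level rule does; read literally, this can only raise the descriptive per-fungus rate or leave it unchanged

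*SAP*

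**What the plan says.** The plan assesses mycological outcome at two levels.

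**Patient level.** Protocol 7.3.7.2 defines "Presumed eradication: In the case when the focus improved and the collection of test material became impossible", and SAP 6.2 repeats this wording. The grade is given at the end of the observation period. Inadequate follow-up and a test that was not done are both Indeterminate. SAP 8.2.4.2 then reports the share of patients whose "mycological response was determined as eradication or presumed eradication", leaving Indeterminate patients out of the denominator.

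**Fungus level.** Later in SAP 6.2, each causative fungus is classed in the safety analysis set. Eradication means a negative fungal volume after treatment "or a specimen cannot be collected". Persistence means a positive volume. The third class begins "Indeterminate: All mycological tests after treatment with Vfend are" and covers tests not performed or a fungal volume that is unknown. SAP 8.2.4.3 divides eradicated fungi by "the number of (eradicated + persistent) fungi", separately for each causative fungus, with a 95% confidence interval. SAP 8.1.3 makes that interval exact.

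**The concern.** The two rules treat the same situation differently. Take a child whose focus has not improved and from whom no specimen can be obtained. At patient level the child does not qualify as presumed eradication. At fungus level, on the literal wording, the fungus is eradicated. It enters both the numerator and the denominator of the per-fungus rate as a success. No other section of either document restores the missing condition. The SAP 8.2.4.3 formula also does not separate negative-test eradication from eradication inferred because no specimen was available, so a reader of the table could not see how much of the rate rests on the second kind.

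What is at stake is one descriptive estimate. It could look better than the evidence allows, and two tables in one report could disagree about the same child. The rate is split by fungus, so individual cells may be small and a single fungus may move a cell visibly.

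**Working it through.** The documents state no value for this rate, so there is no figure to reproduce. All counts below are assumed.

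**Notation.**
- E = eradicated fungi: negative test, or uncollectable with an improved focus
- P = persistent fungi
- u = fungi with an uncollectable specimen and an unimproved focus

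**Formulas.**
- Literal SAP 6.2 rule: (E + u)/(E + P + u)
- With the focus condition, the u fungi being Indeterminate: E/(E + P)
- Difference: [(E + u)(E + P) − E(E + P + u)] / [(E + P)(E + P + u)] = uP/[(E + P)(E + P + u)]

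The difference is never negative. Because P/(E + P) cannot exceed 1, it is at most u/(E + P + u), a bound reached when E = 0. For E + P = 20 the bound is 1/21 = 4.8 points with u = 1 and 3/23 = 13.0 points with u = 3.

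**Assumed examples, E + P = 20** (exact 95% intervals where shown):

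| E | P | With condition | Literal, u = 3 | Rise, u = 3 | Rise, u = 1 |
|---|---|---|---|---|---|
| 18 | 2 | 90.0% | 21/23 = 91.3% | 1.3 points | 0.5 points |
| 15 | 5 | 75.0% | 18/23 = 78.3% | 3.3 points | 1.2 points |
| 10 | 10 | 50.0% (27.2 to 72.8) | 13/23 = 56.5% (34.5 to 76.8) | 6.5 points | 2.4 points |
| 2 | 18 | 10.0% (1.2 to 31.7) | 5/23 = 21.7% (7.5 to 43.7) | 11.7 points | 4.3 points |

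**Small cells.** E = 2, P = 2, u = 1 gives 3/5 = 60% against 2/4 = 50%. E = 0, P = 0, u = 1 gives 1/1 = 100% (2.5 to 100), where the conditioned rate cannot be estimated.

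**When the rise is zero.** It is zero if u = 0 (which includes every uncollectable case having an improved focus), if P = 0 with E > 0, or if the case report form records these specimens as not performed, which SAP 6.2 sends to Indeterminate.

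**Effect of showing uncollectable fungi separately.** Split E = 10 into 7 negative-test and 3 presumed fungi, with P = 10 and u = 3. The literal rate is 13/23 = 56.5%. With the condition it is 10/20 = 50.0%. Without any uncollectable fungi it is 7/17 = 41.2% (18.4 to 67.1).

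**The case against.** The strongest reply is that no bias has been shown. SAP 6.2 separates three states: specimen not collectable, test not performed, and volume unknown. The last two are Indeterminate. The first may be meant as shorthand for the patient-level category, in which sampling became impossible because the focus improved. Whether a specimen missing from an unimproved focus would be recorded as uncollectable or as not performed depends on case report form coding that the documents do not give. This stands: the size is unknown and may be zero. It does not remove the mismatch, because the same section states the condition for one endpoint and omits it for the other, and a programmer will follow the written rule.

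The second reply is that little depends on this rate. Protocol 7.7 names only the clinical response rate and the patient-level eradication rate. SAP 4.1 sets no significance level and SAP 4.2 has no decision rule. The intervals above overlap widely, and the larger rises come from examples with many persistent fungi or very small cells. This also stands, and it limits the severity.

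Third, pooling negative-test and presumed cases is the protocol's own patient-level practice, so pooling in itself is not an error. That is correct. Separate counts are requested for transparency.

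A reader might infer more: that the SAP counts every missing test as a success, or that the study's effectiveness results are inflated. Neither is supported. Tests not performed are excluded from the rate, and the patient-level eradication rate keeps the condition on the focus.

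**Conclusion.** The inconsistency is real and its direction is certain: followed literally, SAP 6.2 cannot lower the per-fungus eradication rate and may raise it. The amount cannot be computed from the documents. With an assumed 20 fungi otherwise eradicated or persistent and 1 to 3 uncollectable from unimproved foci, the four examples give rises of 0.5 to 11.7 points. These figures rest on the assumed counts, on such fungi being coded as uncollectable, and on Indeterminate as their proper class. The effect is confined to this one descriptive rate. The patient-level eradication rate and the clinical response rate do not change, and nothing here shows that a study conclusion would. Severity is minor.

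**What to change.** **SAP 6.2.** Count an uncollectable specimen as (presumed) eradication only if the focus improved, in line with Protocol 7.3.7.2 and judged at the end of the observation period. Otherwise class the fungus as Indeterminate.

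- Where a child has one causative fungus, take improvement from the recorded patient-level grade. If no grade was recorded, class the fungus as Indeterminate. This can happen because the per-fungus endpoint uses the safety analysis set, whereas SAP 5.2.2 limits the mycological analysis set to children for whom "data for mycological response evaluation (mycological response at the end of the observation period) were collected".
- Where a child has several fungi, the single grade may not describe each focus. List the uncollectable fungi individually, for example within the planned "Listing of mycological test" in SAP 9.

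Do not add a rule by which any earlier test result overrides a later uncollectable specimen. The SAP contains no such precedence. It could make a fungus Persistent on an early positive test although the focus later improved and yielded no specimen, contrary to the end-of-observation assessment. With E = 10 and P = 10, moving one such fungus from eradicated to persistent gives 9/20 = 45.0% against 50.0%.

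**SAP 8.2.4.3.** For each fungus, show negative-test, uncollectable/presumed, persistent and Indeterminate counts, and give the rate with and without the uncollectable fungi.

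**Cost.** One derivation rule and some extra columns in one table, with no new data collection. The denominator may be slightly smaller and the rate lower. Presumed eradication may be under-counted in children with several fungi: with E = 10 and P = 10, moving one truly presumed fungus to Indeterminate gives 9/19 = 47.4%, and moving two gives 8/18 = 44.4%, against 50.0%. The individual list makes these cases visible.
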